10.4 Data collection for economic evaluation

The burden of neuropathic pain seems to be related to the complexity of neuropathic symptoms (e.g. allodynia), poor outcomes and difficult treatment decisions. Evidence suggests that herpes zoster and peripheral nerve traumas are the most frequent causes of peripheral neuropathic pain, whereas stroke, multiple sclerosis and spinal cord injury are the major causes of central neuropathic pain. The negative impact upon functioning and quality of life is profound. Studies have demonstrated that neuropathic pain is more severe than non-neuropathic pain. Previous research has shown that NP can be

interfering with sleep, functioning, and emotional well-being. 60-63 It was shown in US patients suffering from painful peripheral neuropathy with small fiber involvement that they experience moderate to severe pain, which negatively impacts health status, function and productivity and leads to substantial direct and indirect costs. 64 In a study in patients suffering from post-traumatic/post-surgical NP it was shown that these patients reported high pain scores, which were associated with poor health utility, sleep, mood and function, as well as high health care resource utilisation and costs. The impact on quality of life and costs attributable to these NP conditions suggest an unmet need and the potential benefits of more effective management of NP. 65

The most commonly used HRQOL (Health-related quality of life) instruments are general, whereas others have been designed specifically for those with neuropathic pain. Meyer•Rosberg and col• leagues validated both the 36•Item Short Form Health Survey (SF•36) and the Nottingham Health Profile (NHP) in the assessment of HRQOL in neuropathic pain related to peripheral nerve or nerve root lesions in patients attending multidisciplinary pain clinics. The scores of all eight dimensions (vitality, physical functioning, bodily pain, general health perceptions, physical role functioning, emotional role functioning, social role functioning and mental health) in the SF•36 were significantly lower in those with neuropathic pain than in the general population, which is in line with another study. Employment status was reduced in more than 52% of these patients.

The onset of neuropathy in patients with diabetes mellitus has been shown to significantly decrease all aspects of quality of life.⁶⁸ If diabetic polyneuropathy is accompanied by pain, both physical and mental components of quality of life are further affected.⁶⁹ A recent study also showed that both EuroQol five dimensions (EQ•5D) and Short Form•6 dimension (SF•6D) questionnaires can discriminate between chronic pain with or without neuropathic pain.¹⁴ Furthermore, the role of psychological factors in impairing quality of life in neuropathic pain has been analyzed, showing, for example, that pain catastrophizing was associated with decreased HRQOL.⁷⁰ The SF•36 and the EQ•5D have been the most commonly used instruments in clinical trials to assess the efficacy of treatments, such as gabapentin in postherpetic neuralgia⁷¹, diabetic polyneuropathy⁷² and neuropathic pain due to peripheral nerve injury⁶⁷; the efficacy of duloxetine in diabetic peripheral neuropathy.⁷³; and the efficacy of spinal cord stimulation in diabetic polyneuropathy.⁷⁴ Finally, it should be mentioned that it has been shown that the EQ-5D seem to have higher construct validity and responsiveness than the SD-6D in patients with chronic pain.⁷⁵

The primary outcome measurement of the proposed study protocol is a measurement of the overall quality of life of these patients suffering from LNP. Current first line (oral) treatment options often result in systemic side effects, decreasing the quality of life of the patients and negatively impact treatment adherence. Significantly decreasing these side effects (by using topical treatment options) will immediately result in a positive impact on QoL of these patients. Positive impact on QoL of patients suffering from LNP will have immediate positive impacts on activities of daily living (e.g. gait, ADLs), will increase and normalize their participation in normal socio-economic activities as well as their employment status. Significantly decreasing the incidence and severity of side effects will enable patients to decrease the number of doctor visits, decrease their medical needs (e.g. physiotherapy, cognitive behavioral support, relaxation), decrease the medical shopping (which is towering in these patients), and decrease the duration of sick leave. In addition, a rapid resolution of the neuropathic pain problem without side effects will also positively impact the use of concomitant medication such as benzodiazepines (great abuse of such drugs in this patient population). Finally, it should be mentioned that some

scientific evidence exists indicating that the painful skin area is actually shrinking during the course of the topical treatment (see above). This means that for example the allodynic area will decrease in size during the course of the topical treatment, something that has never been described with any systemic anti-neuropathic therapy. Allodynia is often a prominent feature of LNP, and is usually considered to be one of the most distressing and debilitating symptoms of PHN. Therefore, one contributory factor to the improved QoL scores is likely to be the reduction in the area of allodynia - typically more than 50% produced by treatment with the lidocaine or capsaicin patch. Reducing the painful area. which can increase tolerance of bathing and contact with clothing, is therefore a justifiable treatment goal for this medication. When the painful area is on the sole of the foot limiting mobility—or on the palm of the hand, this advantage of the topical route over systemic medications assumes even greater importance. Based on the above-mentioned arguments it is obvious that timely implementation (as soon as possible after diagnosis of LNP) of topical treatments can result in significant savings both in the short-term as in the long-term. Recently, a Scottish study stated that capsaicin 8% patch is cost-effective treatment option compared with dose-optimized pregabalin in patients with peripheral NP who have failed one or more previous systemic treatments.⁷⁷

Complexities in the NP care pathway make the condition difficult to manage and difficult to capture in cost-effectiveness models. The authors of this recent review state that to improve future economic modeling in NP, further research is suggested into the effect of multiple lines of treatment and treatment failure upon patient outcomes and subsequent treatment effectiveness; the impact of treatment-emergent adverse events upon patient outcomes; and consistent and appropriate pain measures to inform models. The authors further encourage transparent reporting of inputs used to inform cost-effectiveness models, with robust, comprehensive and clear uncertainty analysis and, where feasible, open-source modeling is encouraged.

10.5 Methodology

The study will possibly include a cost-utility analysis of the topical treatment options compared to standard oral therapeutic approaches (this will be decided after termination of the study and presentation of the findings). This analysis will use cohort simulation based on a Markov model that will be constructed to evaluate the cost- effectiveness of topical lidocaine and capsaicin for the treatment of LNP conditions. Analysis will be performed using a 12-month time horizon from both the payer and societal perspectives, with the latter including indirect costs associated with work productivity and activity impairment that will also be evaluated as a cost component. The model will compare topical treatment to oral systemic treatment by extrapolating effectiveness data for each of the 3 arms in this protocol. Patient-reported outcomes assessments that will be included and incorporated into the economic model will include a numeric rating scale (NRS) for pain severity and sleep quality and the five-level EuroQol health status measure (EQ-5D-5L). Responses on the EQ-5D-5L will be converted to one-dimensional QOL scores using the value set to estimate quality-adjusted life-years (QALYs), which is the unit of incremental cost-effectiveness. The Markov model will follow transition states among severity of no/mild, moderate and severe pain. The pain level at week 26 (end of study protocol) will be extrapolated to 1 year. Resource utilisation in the model, and thus cost inputs, will be estimated through a survey completed by physicians, providing information on treatment of LNP based on longitudinal pain severity transition patterns assuming either moderate or severe pain as the initial pain category. Direct medical costs will be based on resource utilisation and medication use reported by the patients and physicians

(online platform – next generation PELICAN@Home platform). Drug acquisition costs are based on real-world doses observed in previous studies and protocols (see table underneath for medication cost per day).

Table: Medications cost per day (maximum) – 3 treatment groups in study protocol

Lidocaine 5% medicated plaster - VERSATIS	3.28€ per plaster	Up to 3 plasters per day per patient, during 24 weeks	Maximum cost of 9.84€ per day
Capsaicin 8% patch - QUTENZA	308.52€ per patch	Budget 1: Up to 4 patches per patient, max. of 3 applications in each patient (every 90 days)	Maximum cost of 14.70€ per day
	154.26€ per patch	Budget 2: if reimbursement by RIZIV/INAMI; Up to 4 patches per patient, max. of 3 applications in each patient (every 90 days)	Maximum cost of 7.35€ per day (reimbursement category C)
Pregabalin 75mg - LYRICA	0.06€ per 75mg	Up to 8 capsules per day per patient, during 24 weeks	Maximum cost of 0.48€ per day
Gabapentin 300mg – EG	0.05€ per 300 mg	Up to 7 capsules per day per patient, during 24 weeks	Maximum cost of 0.30€ per day

The costs detailed in this table are based on the current reimbursement policies and do not take into account eventual reimbursement by RIZIV/INAMI for the patients participating in this trial.

Indirect costs associated with lost productivity at work will be calculated using the method of Lofland et al.⁷⁹, based on the Work Productivity and Activity Impairment (WPAI) scale for special health problems.^{80,81} In this protocol the WPAI scale for Neuropathic Pain will be applied (v2.2 – Belgium with validated Dutch and French translations available). Productivity will be defined as a percentage from 0% to 100% and mapped to pain scores such that for each point change in pain score, the change in lost productivity can be estimated. Costs will be estimated on mean monthly income in Belgium.

QALYs

For calculation of the cost-utility, estimates of QOL scores for determination of QALYs were based on regression equations with the pain NRS scores, age, and sex as independent variables. These values, estimated individually for males and females, were then weighted and averaged by sex ratio and average age to derive weighted averages for each NRS score.

Cost-utility

Based on QALY and costs, the incremental cost-utility ratio (ICUR) will be calculated to evaluate the cost-utility of topical treatments. Sensitivity analyses will be performed to account for uncertainties in the data sources and assumptions, and to confirm the robustness of the ICURs estimated in the base case.

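### Section 10.5 gives two unreconciled routes to the QALY, and the pain-based one drops any difference between arms that does not run through pain

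*Protocol*

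**What the plan says.** The economic analysis is optional: "The study will possibly include a cost-utility analysis of the topical treatment options", with the decision left until the study has ended and its findings have been presented (section 10.5). If run, it is a cohort model with a 12-month horizon: "The Markov model will follow transition states among severity of no/mild, moderate and severe pain". Pain at week 26 is carried forward to one year.

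On utilities, section 10.5 first says: "Responses on the EQ-5D-5L will be converted to one-dimensional QOL scores using the value set to estimate quality-adjusted life-years (QALYs". No value set is named. Under its QALYs subheading it then says that "estimates of QOL scores for determination of QALYs were based on regression equations with the pain NRS scores, age, and sex as independent variables", and that the resulting values were "weighted and averaged by sex ratio and average age to derive weighted averages for each NRS score". On robustness it says: "Sensitivity analyses will be performed to account for uncertainties in the data sources and assumptions".

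Section 10.4 gives the expected mechanism: "Significantly decreasing these side effects (by using topical treatment options) will immediately result in a positive impact on QoL of these patients". It also cites a review of cost-effectiveness models in neuropathic pain that asks for further research into, among other things, "the impact of treatment-emergent adverse events upon patient outcomes".

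The EQ-5D-5L is scheduled at baseline and at weeks 6, 10, 14, 18, 22 and 26 (section 7.8). Section 3.3 chose it partly because it converts readily to utilities. Section 10.3.3 already plans a per-patient area under the quality-of-life curve by the trapezium rule.

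**The concern.** The two descriptions of the QALY are left side by side with nothing to connect them. Section 10.5 does not state the outcome of the regression, the data it was fitted to, or which description governs the base case. Because the decision to run the analysis comes after the results are known, a choice between the two would also be made with the results in view.

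The larger issue is what the second description can register. A utility that depends only on the pain score cannot tell a patient with dizziness or somnolence from one without, at the same pain. The protocol's argument for topical treatment rests in good part on avoiding such effects (sections 2 and 10.4), and its planning figures in section 10.1 show study-drug withdrawal of 18.6% on pregabalin against 5.8% on lidocaine and 2.1% on capsaicin. A cost-utility analysis built on the second rule would leave out a benefit that the trial was partly designed to show.

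**Working it through.** The protocol states no QALY or incremental cost-utility ratio (ICUR), so there is no figure of its own to reproduce. The check compares the two rules, then uses algebra and a simulation on assumed values.

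**1. The two rules in section 10.5**

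| | First rule | Second rule |
|---|---|---|
| Source of utility | Each patient's EQ-5D-5L responses | Regression on pain NRS, age and sex |
| Dependent variable | Not applicable (value set applied to responses) | Not stated |
| Data | This trial | Not stated; written in the past tense |
| Final utility varies with | Whatever the five dimensions register | Pain score only, after averaging over sex and age |
| Named as base case | No | No |

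**2. Joining them.** Suppose the trial's EQ-5D-5L index is the regressed outcome. After averaging there is still one utility per NRS score, so arm and side effects remain invisible at equal pain.

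**3. Nothing else in section 10.5 restores the loss.** The model states are pain severity, no adverse-event disutility is mentioned, and lost productivity is also mapped to pain scores.

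**4. Algebra.** Let P be the utility difference (topical minus pregabalin) that runs through pain, and E the difference that does not. Assume age and sex are balanced by randomisation.

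- Measured gain = P + E; mapped gain = P.
- With s = E/(P + E), mapped gain = (1 − s)(P + E).
- The utility rule leaves incremental cost unchanged, so mapped ICUR ÷ measured ICUR = (P + E)/P = 1/(1 − s).

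For a positive measured gain and a higher cost of topical treatment:

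| s | Factor on the ICUR |
|---|---|
| 0 | 1 (no bias) |
| 0.25 | 1.33 |
| 0.50 | 2 |
| 0.75 | 4 |
| 1 | undefined (mapped gain is zero) |
| above 1 (pain favours pregabalin) | negative: topical appears dominated |
| below 0 (net disutility worse on topical) | below 1: bias reverses |

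An example of the last row, with assumed values: P = 0.04 and E = −0.01 give 0.03/0.04 = 0.75.

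**5. Simulation, all values assumed.** Side effects occur in 45% on pregabalin and 5% on topical treatment, cost 0.10 of utility, and are unrelated to pain within an arm. Utility falls by 0.05 per NRS point. The side-effect component is (0.45 − 0.05) × 0.10 = 0.040. Utility was regressed on NRS, age and sex with no arm term.

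| Pain difference | Measured utility difference | Mapped utility difference |
|---|---|---|
| None | 0.040 | 0.000 |
| Topical better by 0.5 points | 0.065 | 0.025 |
| Topical worse by 0.5 points | +0.015 | −0.025 |

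In every row the gap is 0.040, the whole side-effect component. In the second row the factor is 0.065/0.025 = 2.6. In the third the sign changes.

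**The case against.** A reader might infer that the two definitions are incompatible. The text does not establish that. A cohort model with pain-severity states needs a utility for each pain level. The section can be read as one pipeline: responses to index, index regressed on pain, then a utility per pain score. The past tense hints at equations estimated elsewhere but is weak evidence. This objection stands as far as it goes: the routes are unreconciled, not shown to conflict. It does not rescue the mapping, because the pipeline also ends with a utility that depends on pain alone.

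A reader might also infer that the ICUR of topical treatment would certainly be too high. That is conditional. The mapping must be the base case, side-effect disutility must be greater on pregabalin, and the mapped gain must stay positive. The background section reports that the lidocaine plaster failed to demonstrate non-inferiority in its one direct comparison with pregabalin, so a mapped gain at or below zero is plausible. Capsaicin causes its own skin reaction (section 7.4), so the net direction for that arm is not established either.

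Finally, the analysis may never be run, general sensitivity analyses are promised, and the area-under-the-curve comparison in section 10.3.3 would show the directly measured result. All of this limits the consequence. But the sensitivity sentence does not name the utility source, and a separate secondary analysis does not correct a modelled QALY.

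**Conclusion.** The point holds in a conditional form. Section 10.5 describes two routes to the QALY without saying how they relate. The pain-based one, on either reading, removes any utility difference between arms that does not run through pain. Under the protocol's own premise that side effects weigh more on pregabalin, the incremental QALY of topical treatment is understated. The effect on the ratio is then a factor of 1/(1−s) while the mapped gain is positive, and a change of sign or an undefined ratio otherwise. The opposite premise reverses the bias.

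It is tempting to turn this into euros per QALY from the maximum daily drug costs and the planning effect of 0.08. The protocol does not support that. It gives no value for s, plans a 12-month horizon, bases drug costs on real-world doses and includes other direct and productivity costs. The 0.08 is a 4-week published difference. The simulated figures above show the mechanism only. The primary endpoint and its analysis are unaffected.

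**What to change.** If the cost-utility analysis is run, rewrite the utility paragraphs of section 10.5 before results are seen:

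- **Base case, 26-week trial period:** use the measured EQ-5D-5L index by arm, as a baseline-adjusted area under the curve, with the value set named.
- **Pain-to-utility mapping:** use it only for extrapolation from week 26 to 12 months, or as a sensitivity analysis. State its dependent variable and data source, and include a treatment-arm or side-effect term.

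No new data are needed. The cost is a small change to how utilities enter the Markov model, because they would no longer be attached to pain states alone during the trial period.

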11 DATA HANDLING

11.1 Data collection tools and source document identification

There are two primary sources for the trial data. For clinical findings, observations, laboratory data, etc., the participating site's (electronic) medical record will be used as a primary source. For questionnaires completed by the participants, the **PELICAN@Home platform or paper questionnaires** will be the primary source.

In order to allow Source Data Verification of the medical record primary source, each participating site will be requested by the Sponsor to complete, before FPFV in the site, an Electronic Medical Record/Source Data Questionnaire. In this questionnaire, sites will confirm the presence of documentation related to validation of the electronic medical record or other records or questionnaires used as the primary source of trial data. If the participating site is able to provide a System Validation Certificate, a copy will be sent to the Sponsor and stored in the Investigator Site File. This questionnaire will request details concerning (at least) the following topics:

- System validation
- Electronic signature
- System access for monitors, auditors, and inspectors
- Copying, printing, and scanning
- · Backup and archiving

In order to assess the validity of the data collected in the PELICAN@Home platform, third party BeWell Innovations will be asked to issue documentation related to storage of source data, system validation, backup, archiving, before FPFV in the trial and at the request of the Sponsor. BeWell Innovations will update the documentation and communicate with the Sponsor in case of any fundamental changes or data breaches. The Sponsor and BeWell Innovations will agree on timings and format of the release of source data to the sponsor/CI. A copy of the source data of all patients in PELICAN@Home included at a specific site will be provided to the local investigator.

An electronic case report form (eCRF) system – i.e. OpenClinica Community Edition – will be used by all participating sites to collect the individual patient data required by the trial protocol. It will include data from the (electronic) medical record(s) (primary source 1) and from the PELICAN@Home platform (primary source 2). The eCRF data will be used to perform the statistical analyses for the trial, as described in Section 10.3.

The Sponsor will provide functional training for designing eCRFs in and extracting data from OpenClinica for (at least) the Chief Investigator, the Trial Coordinator, and the Data Manager. The Sponsor will provide data entry training sessions for the participating centers. The training sessions will be repeated if necessary (e.g. new version, delayed data entry, ...) The Sponsor designates the Chief Investigator and the statistician to validate the designed eCRFs to ensure that the data points required for statistical analysis for the trial are included and no redundant or secondary data is being collected. Validation of the designed eCRFs is done by means of a paper print with wet signature by both Chief Investigator and statistician. In case of changes in the design of the eCRFs, the validation

is repeated. Full audit trail of data collected is available in OpenClinica. The Chief Investigator, Trial Coordinator, Data Manager, monitors, and auditors will receive access to the audit log in OpenClinica. Data extraction can be performed by the designated people at fixed times.

The eCRF system will not be used as a primary source of data.

11.2 Data handling and record keeping

The **PELICAN@Home platform** (developed by the Antwerp University Hospital in cooperation with BeWell Innovations) – a primary source – is hosted on servers within the central server facility at the Antwerp University Hospital (Sponsor's location). The use of this platform has become routine standard care since the platform is used nationwide for other (pharmacological and invasive) therapeutic options for severe chronic pain conditions in all acute Belgian hospitals. This nationwide access to the online platform was fully implemented by February 1st 2018.

All trial data will be gathered in OpenClinica (Community Edition), an open-source webbased electronic Case Report Form (eCRF) system. The Sponsor hosts OpenClinica version 3.13 on two virtual servers – one for the initial testing of the eCRFs and one for the collection of trial data in production. These virtual servers are hosted in the central server facility at the Antwerp University Hospital (Sponsor's location). The trial data are backed up on a daily basis and stored in a Data Domain (Dell EMC Data Domain) at the Sponsor's location to enable disaster recovery with a maximum loss of 1 day of trial data. The Sponsor's IT project lead who supports OpenClinica is certified to provide basic and advanced training in OpenClinica version 3.13 to end users. Since the eCRF data are stored at the Sponsor's location, no data storage needs to be foreseen with the participating sites.

PELICAN@Home and paper questionnaires data will be integrated into OpenClinica.

In the eCRF, the trial participants will be coded by their unique enrolment ID.

The sponsor will be responsible for data analysis after the monitoring has been concluded.

